21.0 POTENTIAL BENEFITS

This study is designed to identify a non-opioid detoxification medication protocol that is easy to use, does not require special licensing, and can increase the chances that opioid addicted patients are able to transition to naltrexone. If hypotheses are confirmed the study will have identified a medication that is more effective than current options for detoxifying opioid addicted patients.

22.0 CONFIDENTIALITY

22.1 HIPAA COMPLIANCE

All research staff have HIPAA training, support the privacy of clinical and research data collected as part of any study, and follow NIH policy in use and disclosure of protected health information in a manner that respects privacy in accord with the "Privacy Rule" under the Health Insurance Portability and Accountability Act (HIPAA) and other applicable laws. All subjects sign a HIPAA-authorization form, receive a copy of this form, and receive a notice of the site's privacy practice. HIPAA signed forms are retained in locked file cabinets with patients' source documents.

Information about study subjects will be kept confidential and managed according to requirements of the Health Insurance Portability and Accountability Act of 1996 (HIPAA). Those regulations require a signed subject authorization informing the subject of the following:

- What protected health information (PHI) will be collected from subjects in this study
- Who will have access to that information and why
- Who will use or disclose that information

The rights of a research subject to revoke their authorization for use of their PHI.

In the event that a subject revokes authorization to collect or use PHI, the investigator, by regulation, retains the ability to use all information collected prior to the revocation of subject authorization. For subjects that have revoked authorization to collect or use PHI, attempts should be made to obtain permission to collect at least vital status (i.e. that the subject is alive) at the end of their scheduled study period.

No information about subjects will be disclosed to others without the subject's prior written permission, except as stated in the informed consent, or if necessary to protect the rights or welfare of a subject in accordance with the law. Names or unique identifying information are never used in the publication of research data. Procedures designed to maintain confidentiality include: (1) formal training for all research staff on the importance of confidentiality; (2) procedures to protect a patient's confidentiality; and (3) formal mechanisms limiting access to information that can link data to individual patients. Data forms that include identifying information are kept in locked cabinets. Only the unique identification (ID) number, assigned at the time of initial contact represents patients during data entry, data transfer, analyses, or other file management procedures. To facilitate tracking, a password-protected computer file on a secure server is maintained containing the identity of patients, ID numbers, and information about how they can be reached. This file, however, contains no clinical data. All data are stored in a securely locked area accessible only to authorized research personnel. The Principal Investigator (PI) is required to allow trial-related monitoring, audits, IRB review, and regulatory inspection by providing direct access to source documents. The FDA, IRB, and other regulatory authorities will also have access to source documents. We inform subjects of this access in the informed consent. HIPAA regulations are followed.

23.0 INDEPENDENT DATA AND SAFETY MONITORING BOARD

23.1 DESCRIPTION

A safety monitoring board has been established at the Center for the Studies of Addiction with the following purpose (according to NIDA guidelines): to assure that the safety of study subjects is protected while the scientific goals of the ongoing studies are being met. The DSMB is charged with monitoring safety of participants and quality of the data, as well as the appropriate termination of studies when significant benefits or risks have been uncovered or a clinical trial cannot be concluded successfully.

23.2 BOARD MEMBER QUALIFICATIONS

All board members will meet NIDA requirements regarding background and experience, and none will have ethical conflicts, including financial interest related to study outcome. Individuals invited to serve on the board will disclose any potential conflicts in writing. The board will meet every six months (unless more frequent meetings are deemed necessary) and will be chaired by [name]., a faculty member within the Department of Psychiatry at the University of Pennsylvania. Other members of the board include faculty of the University of Pennsylvania School of Medicine, Department of Psychiatry.

When the current study is reviewed, [name] will prepare and submit a summary report on the trial status, followed by a closed session under the direction of [name]. Issues related to recruitment, subject safety and efficacy, whether the primary study question is being answered, conflict of interest, confidentiality, and ongoing study review (including AEs, SAEs, and regulatory issues) will be assessed. Following each DSM Board meeting, [name] will make recommendations to [name], and a final report (edited by all Board members) will be prepared and submitted to NIDA, the Penn IRB, and (if required) the FDA. In addition to semiannual reviews, at the occurrence of

the second medication associated serious adverse event or after the first fatal medication associated adverse event the protocol will be reviewed by the DSMB to consider modifications to the protocol or discontinuation.

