3.0 PROTOCOL SUMMARY

Title	Combining Pregabalin (LYRICA®) with Lofexidine (LUCEMYRA™): Can it Increase the Success of Transition to Naltrexone?						
Short Title	Pregabalin and Lofexidine for opioid withdrawal						
Protocol Version	7.0						
Phase	Phase 2						
Methodology	Double-blind placebo-controlled parallel group clinical trial						
Study Duration	24 months						
Study Centers (3)	 University of Pennsylvania Center for Studies of Addiction in Philadelphia Pennsylvania Columbia University in New York City, New York Mountain Manor in Baltimore, Maryland 						
Objective (Primary)	To investigate whether pregabalin-Lyrica® (PGB) combined with Lofexidine-Lucemyra® (LFX) can reduce opioid withdrawal-related subjective effects						
Objective (Secondary)	To investigate, if the PGB/LFX combination can increase the proportion of patients with an opioid use disorder (OUD) who complete detoxification and transition to antagonist treatment with extended- release injectable naltrexone VIVITROL® (XR-NTX)						
Number of Subjects	90 subjects. 60 randomized to PGB/LFX; 30 to PGB-PLA/LFX						
Inclusion Criteria	 Male and/or female subjects ≥ 18 years of age Meet DSM-5 criteria for an Opioid Use Disorder with physiologic features. Have 2 or more of the 11 DSM 5 criteria for opioid disorder including tolerance and withdrawal features in the last 12 months Interested in opioid antagonist treatment Have used opioids in 20 of the past 30 days Have a stable address in the local area; not planning to move; have documents for ID check Absence of medical or psychiatric conditions that are likely to interfere with study participation Have a 12 lead ECG demonstrating a QTc ≤450 msec and a QRS interval ≤120 msec. The site PI has the final determination for inclusion into the study for ECGs unless there is a question of QT prolongation or other factors (QTc/Fri uses the Fridericia formula (QTc = QT/RR(1/3)). If consultation is needed, the PENN cardiologists and the medical monitor should be contacted. If female, have a negative pregnancy test, and uses adequate contraception if of childbearing potential 						

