Note: Study medication will be provided in blister packs that are prepared by the PENN Investigational Drug Service and shipped to all three study sites. For the University of Pennsylvania, each blister pack will have a patient randomization number and the dosing schedule for each time on each inpatient study day, as summarized in the Study Schematics 4.0 below. For the two external sites, patient randomization will be generated by the site pharmacy or designated unblinded person, who receives the blister packs from the PENN Investigational Drug Service with the dosing schedule for each day.

The doses for each time of each day will be in separate compartments. Lofexidine will be 0.18 mg pink tables; pregabalin or pregabalin placebo will be in capsules. Blue capsules will contain 100 mg pregabalin or placebo; green capsules will contain 25 mg pregabalin or pregabalin placebo. These medications have not been used together and it is likely that doses will need to be held or reduced due to side effects. The most likely side effect from lofexidine is hypotension and/or bradycardia. The most likely side effect from pregabalin is sedation. Thus, in the event of hypotension, the next scheduled dose of lofexidine can be reduced or withheld. A similar adjustment can be made for excessive sedation (POSS score of 3 or 4; difficult to arouse, slurred speech, etc.) For the PENN site, medication counts will be done by the Investigational Drug Service (IDS) pharmacy for each subject. For sites outside PENN, medication counts will be done by the site or site pharmacy.

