9.0 STUDY DESIGN

This study is a phase II, two-part randomized, double-blind placebo-controlled, study to assess the effectiveness of PGB combined with LFX to reduce opioid withdrawal- related subjective effects, and to examine whether a PGB/LFX combination can increase the proportion of opioid use disordered (OUD) subjects who transition to antagonist treatment (XR-NTX).

The study will use three sites, each with inpatient units that provide beds and care from nurses that will be trained in study procedures and dosing requirements. Each site will recruit around 30 randomized subjects, with the Mountain Manor Site and the PENN site possibly recruiting greater than 30 subjects, for a total sample size of 90, using DSM-5 to establish an OUD diagnosis with physiologic features. This trial has 4 distinct phases (see Figure 1 schematic): 1) Outpatient Screening; 2) Inpatient medication induction plus other assessments on Days 1-7; 3) Inpatient XR-NTX administration on Day 8 or 9; and 4) Outpatient Follow-Up (5 days). Total days in study is 15 days plus or minus the time taken to complete the initial outpatient screening assessments. Randomization will occur before inpatient admission.

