16.2 MONITORING VISITS

Monitoring will be conducted in accord with University of Pennsylvania Sponsor-Investigator Standard Operating Procedure PM 504. Enrollment will be complete when 90 patients are randomized into the trial. Approximately 2 patients/site will be randomized per month and monitoring visits conducted periodically throughout the study. The first visit will occur no more than two weeks after the first patient is entered. Subsequent visits will be conducted guarterly, as described below.

- Visit 1: Initiation Visit
- Visit 2: Approximately 25% of subjects to be randomized have completed the trial and 100%
 Source Document Verification for the first two randomized subjects
- Visit 3: Approximately 50% of subjects to be randomized have completed the trial.
- Visit 4: Approximately 100% of subjects to be randomized have completed the trial. This visit serves as the closeout-monitoring visit.

If a greater than 10% error rate is noted during the data review, the monitor will source data verify 100% of the data on a larger sample at the following monitoring visit

16.3 **MONITORING LOG**

At the beginning of each monitoring visit, the monitor and any representative of the Sponsor participating in monitoring must sign and date the monitoring log.

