19.0 STOPPING RULES

19.1 STUDY STOPPING CRITERIA

In addition to oversight by the University of Pennsylvania IRB and Office of Human Research,

the trial will be conducted under the supervision of a Data Safety and Monitoring Board, as outlined below in section 8.6.1. This independent board will review the study every 6 months. The DSMB is charged with monitoring the safety of participants and the quality of the data, as well as the appropriate termination of studies either when significant benefits or risks have been uncovered or when it appears that a clinical trial cannot be concluded successfully. The DSMB will review all adverse events and will have access to unblinded data in order to determine the association between adverse events and study medication. If a pattern of significant adverse events is uncovered that suggests that the risks of continuing the trial outweigh the expected benefits of the trial then the DSMB will recommend that the study be stopped.

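### The unscheduled DSMB triggers in 23.2 count only deaths and SAEs already called medication associated, name no assessor, and have no SAE reporting route to the board behind them

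*Combined protocol and SAP*

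**What the plan says.** **Scheduled reviews.** Section 19.1: "This independent board will review the study every 6 months". Section 23.2 leaves room for more: "The board will meet every six months (unless more frequent meetings are deemed necessary"). No board review is tied to a number of patients treated.

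**Unscheduled reviews.** Section 23.2 adds a review after "the second medication associated serious adverse event or after the first fatal medication associated adverse event the protocol will be reviewed by the DSMB". It does not say who decides that an event is medication associated, or by what standard.

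**Who judges association.** Under 19.1 the DSMB "will have access to unblinded data in order to determine the association between adverse events and study medication". Section 15.8 also requires the investigator's assessment of association in each initial SAE report, and 13.7 records relatedness for each AE. Section 18.3 keeps all research staff blind until the study ends, apart from emergency unmasking of single patients.

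**Where SAE reports go.** Sections 15.7 to 15.12 name the IRB, NIDA, the sponsor, the medical monitor and the FDA. They do not name the DSMB.

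**The setting.** Section 3.0, on the two study drugs: "These medications have not been used together and it is likely that doses will need to be held or reduced due to side effects".

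**The concern.** Section 23.2 calls the board in early so that someone with unblinded data can look at a worrying event. Both triggers, however, depend on a causal label attached before the board sees anything. The label on record comes from a blinded investigator. That person is judging one case at a time, for a combination with no previous experience, in patients whose opioid withdrawal can offer another explanation.

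If the site calls a death unrelated, the fatal-event trigger does not apply. If it calls one of two SAEs unrelated, the two-event trigger does not apply. With no SAE route to the board, nothing in the reporting sections tells the board that a discretionary meeting might be needed.

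Section 7.1.6 wants a combination that produces no more SAEs than lofexidine alone. That is a comparison between arms, which blinded attribution of single cases cannot make. The DSMB is the only body that the documents describe as reviewing adverse events on unblinded data.

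**Working it through.** The plan states neither the exposure at the first board review nor a probability that the trigger fires, so there is no figure of its own to reproduce.

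**1. Exposure at a six-monthly review**

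Inputs:
- Accrual: "Approximately 2 patients/site will be randomized per month" (16.2).
- Sites: three (9.0).
- Allocation: "90 subjects. 60 randomized to PGB/LFX; 30 to PGB-PLA/LFX" (3.0), so two thirds receive the combination.
- Alternative accrual: 90 patients over the 18-month recruitment window in 10.3.2, or 90/18 = 5 per month.

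Results:
- At the 16.2 rate: 3 × 2 × 6 = 36 randomised; 36 × 60/90 = 24 on PGB/LFX; 24/60 = 40% of that arm.
- At the timetable rate: 5 × 6 = 30 randomised; 30 × 60/90 = 20 on PGB/LFX; 20/60 = 33%.

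These are upper values, because they put the first meeting a full six months after the first patient. A meeting at month three gives 5 × 3 × 2/3 = 10 to 6 × 3 × 2/3 = 12.

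**2. Chance that the two-SAE trigger has fired by then**

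The trigger is not limited to one arm, so all randomised patients count. The documents give no SAE rate, so p, the proportion of patients with a medication-associated SAE, is an assumed range. The model takes at most one SAE per patient, independence, the same p in both arms, and full follow-up of everyone randomised by month six.

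P(at least 2) = 1 − (1 − p)^n − n·p·(1 − p)^(n − 1)

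For n = 36 and p = 0.05: 1 − 0.158 − 0.299 = 0.543.

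| Assumed p | n = 36 | n = 30 |
|---|---|---|
| 1% | 5% | 4% |
| 2% | 16% | 12% |
| 5% | 54% | 45% |
| 10% | 89% | 82% |

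The chance is even at p of about 4.6% (n = 36) or 5.5% (n = 30).

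**3. What the attribution filter adds (n = 36)**

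Suppose half of all SAEs are called medication associated (assumption).
- All-cause rate 10%: the chance of firing falls from 89% to 54%.
- All-cause rate 5%: it falls from 54% to 23%.

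Even with every SAE counted, a 5% all-cause rate leaves the trigger silent by month six in 46% of trials. The filter adds to the delay. The two-event threshold and the calendar interval account for the rest.

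**The case against.** **The rule is not circular.** A reader might infer from 19.1 that only the board may decide association, so that the trigger could never fire before the board has met. The text does not support this. Section 19.1 gives the board unblinded data but does not reserve the judgement to it, and the trigger can fire on the investigator's label. What stands is an unnamed assessor and, in practice, a blinded one.

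**There are other safety looks.** A reader might infer that nobody independent looks at safety before month six. That is too strong.
- Section 23.2 allows extra meetings, and 19.1 has the board review all adverse events.
- Section 15.11 sends all SAEs to the IRB (15.7 is narrower), and 15.9 sets reporting times for deaths, including unrelated ones.
- The medical monitor regularly assesses SAEs (17.1).
- Monitoring reports are copied to the DSMB (16.4). Monitoring visit 2 falls at about 25% completion: 0.25 × 90 = 22.5 patients, about 15 of them on PGB/LFX.
- Patients are inpatients with daily ECGs and frequent vital-sign and sedation checks (9.1.2).

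All of this stands as mitigation. But the IRB, medical monitor and monitoring routes are not described as comparing SAEs by arm, extra board meetings are discretionary, and 19.1 gives no time limit for an individual SAE to reach the board. A monitoring plan on file with NIDA (section 24.0) is not in these documents and may say more.

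**The numbers depend on an assumption.** It is tempting to say that the trigger will often stay silent. That holds at low SAE rates and fails at 10%. Counting only the 24 combination patients would also understate the trigger: at 5% it gives 34%, against 54% on all 36, because placebo-pregabalin patients count too.

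**Conclusion.** The concern holds in a limited form. Both unscheduled triggers depend on an attribution whose assessor 23.2 does not name. The only attribution on record before a board meeting is a blinded one, and the reporting sections do not bring SAEs to the board. A death or SAE called unrelated therefore does not prompt the unblinded review described in 19.1.

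The exposure at stake is up to 20 to 24 patients on the combination, a third to two fifths of that arm, before the first scheduled review. It is lower if the standing board meets earlier. How likely the trigger is to fire sooner cannot be settled from the documents: the range is about 5% to 89% for assumed rates of 1% to 10%.

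This is an inexpensive improvement to a stated rule. It does not show that the trial lacks safety oversight.

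**What to change.** 1. **Section 23.2:** convene an unscheduled DSMB review on any death, and on the second SAE of any attribution, from first dose to last follow-up. The board then judges association on unblinded data, as 19.1 provides. The window should not close at Day 9: the present rule has no such cut-off, and one would drop non-fatal SAEs arising after XR-NTX.
2. **Section 15.8:** add the DSMB chair to the SAE distribution.
3. **Optional:** set the first scheduled review by exposure as well as by calendar, for example when about 15 randomised patients (about 10 on PGB/LFX) have passed Day 9. Ten exposed patients give a 1 − 0.85^10 = 80% chance of seeing at least one event whose true frequency is 15%. The exact number is the sponsor's choice. This step matters because, as step 3 of the working shows, dropping the attribution filter does not by itself guarantee an early look.

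The cost is protocol wording and possibly one or two board reviews for events that prove unrelated, plus one earlier review if the option is taken. No patients or study procedures are added. The reviews concern safety only, so no alpha is spent.

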24.0 DSMP STUDY MONITORING PLAN

This study has a monitoring plan on file with NIDA. The investigator will allocate adequate time for such monitoring activities and also ensure that the monitor or other compliance or quality assurance reviewer is given access to all the above noted study-related documents and study related facilities (e.g. pharmacy, diagnostic laboratory, etc.), and has adequate space to conduct the monitoring visit.

25.0 COVID SAFETY PLAN

a. Risk for COVID Procedures:

1. COVID PRECAUTIONS - University of Pennsylvania

- I. When you bring your study subjects in for their visit to 3535 for their screening visit, you should perform a nasal swab for ROUTINE SARS-CoV-2 testing. This should be ordered and sent to the Presby lab. The results will be back within 24 hours.
- II. The Director of Infection Control at PPMC, and the Infection Control team will provide guidance to the 4WS and 5 WS units on best practices for screening and managing the patients. The Infection Preventionist staff person is tasked with oversight for IC related topics for Behavioral Health.
- III. Through the Infection Preventionist staff person, the infection Control team will alert WS 4 team that a test within 24-48 hours is acceptable within the context of your planned study admissions.
- IV. Once the patient is admitted, they will be quarantined for 72 hours in a single room, retested, and if negative, will then be released from quarantine into a semi private room.

2. COVID PRECAUTIONS - MOUNTAIN MANOR Treatment Center

I. Outpatient Screening

Standard Covid screening questions and Covid testing will be incorporated into the screening visit. Study staff will follow standard infection control procedures including wearing masks and distancing, during consent and assessments.

II. Treatment center admission

Patients receive Covid screening questions and Covid testing on the day of admission. Admitted patients are admitted in cohorts, separated from the general treatment population until Covid results are known. Patients who test Covid negative are integrated into the general treatment population. Patients who test positive are placed in medical isolation until an appropriate disposition can be arranged. Study staff and usual care clinical staff follow standard infection control procedures including wearing masks, use of other PPE as appropriate, and distancing.

III. Post discharge follow-up

Any post discharge study assessments may be obtained remotely by telehealth platform as appropriate.

3. COVID Precautions - Columbia University

There are risks of exposure to coronavirus 2019 (COVID-19). At this time, there is still a significant risk of infection from COVID-19 whenever entering a public setting or interacting with others.

Participation in this research study also carries additional risks. We will discuss additional risks due to COVID-19 with participants prior to beginning the study. NYSPI will test for COVID-19 prior to any participant entering the unit and also on the first day when a participant enters the unit. Please see COVID-19 test SOP. Below are additional precautions we are taking due to COVID-19.

I. All research at NYSPI has been modified to reduce in-person visits and procedures.

- We now use technology (telephone and computer) to perform all possible research procedures (such as obtaining consent, clinical interviews, symptom scales, and other tests) remotely.
- We are recommending that only tests and procedures that cannot be performed remotely should take place in-person. If the participant prefers an in-person meeting for a specific visit or procedure, we encourage him/her to discuss this possibility with the study team.

II. We are monitoring research participants and staff for signs and symptoms of COVID-19.

- The participant will be contacted by study staff on the day prior to your visits and asked whether they have any symptoms consistent with COVID-19. Upon their arrival to NYSPI, we will again ask the participant questions about any possible COVID-19 symptoms and take their temperature.
- If they are having any symptoms of COVID-19, we will postpone the visit and recommend that they see a medical professional for evaluation.
- All staff are required to self-monitor themselves for any possible symptoms of COVID-19 and are instructed to stay home and not come to work if they are sick in any way.

III. We are taking extra precautions at NYSPI to reduce the risk of COVID-19 infection.

- When the participant enters NYSPI, he/she will be required to wear a face covering. If they do not have one, they will be given a surgical face mask.
- Staff will wear masks and other personal protective equipment as appropriate to the procedure (e.g., gowns, gloves).
- The participant will be asked to maintain physical distancing (at least 6 feet space between them and other people) while at NYSPI where possible unless specific research procedures require temporarily being closer to study staff.
- Alcohol-based hand sanitizer will be provided at the building entrance and many other areas.
- We are restricting visitor access to only those who are essential for our participants' care.
- Visitors will be screened for fever and symptoms of COVID-19 prior to entry and will be asked to wear face coverings and limit their movement within NYSPI.

IV. We have increased our routine cleaning and disinfection procedures in order to further protect research participants and staff from COVID-19 at NYSPI.

- All equipment used by participants (e.g., blood pressure cuffs, EKG machine) will continue to be thoroughly disinfected before and after each participant's use.

V. Procedures for admission to the inpatient unit:

- All participant must present to the unit with evidence of a negative COVID test. On the day of admission the participant will be brought directly to the back of the dorm area. The participant must be wearing a mask and will be assigned to a single room. The participant will remain in this room for at least the first 24 hours. All meals will be brought to them by unit staff, any assessments will be done in their room with staff wearing PPE, and they can have their telephone during that time so they can call family/friends and play games. Of note, the telephone will not be available after the first 24 hours. There will be no smoking breaks escorted by research staff until after the 24 hour isolation period is complete. After the first 24 hours staff will provide a new mask to them daily which they are encouraged to wear at all times while in public places.
- Upon admission, the unit staff will send off a COVID nasal swab to New York Presbyterian for analysis. Once that returns negative and 24 hours has elapsed the participant can enter

the day area. If the COVID test is positive 1) research procedures will be halted, and 2) a clinical decision involving the Clinical Director will be made regarding appropriate next steps.

The participant will be made aware that they will also have a COVID antibody (serum) test drawn soon after admission. They will have an additional nasal swab COVID test prior to discharge from the unit.

